## 3.4 Subject Withdrawal Criteria

[figure not shown]
There are no foreseeable situations where subject withdrawal should be required. Withdrawal of a subject from the study will be at the Investigator's discretion with consideration of the safety and well-being of the subject.

## 3.5 Study Design

This is a multi-center, open-label study to evaluate use of the Saranas EBBMS for detection of access site-related internal bleeding events during large-bore endovascular procedures.

After signing consent subjects will undergo screening procedures and be scheduled for their endovascular procedure. The endovascular procedure will be performed per the institution's standard practices, with inclusion of monitoring using the Saranas EBBMS. Following completion of the procedure subjects will continue to be monitored using the Saranas EBBMS for internal bleeds for up to 8 hours. The EBBMS will then be removed. A flowchart is provided in **Figure 6**. Adverse events and device effects will be recorded from enrollment of subjects and throughout the procedure, until discharge of subjects.

**Figure 6. Study Flowchart**

### **3.6 Study Procedures and Assessments**

The following procedures and assessments will be performed during the study. For the Schedule of Events see [Table 1](#).

#### **3.6.1 Laboratory Assessments**

- Blood Chemistry: creatinine,
- Hematology: CBC, PT, PTT, INR

#### **3.6.2 Subject Monitoring and Care**

The institutions standard of care monitoring procedures and post-procedural care practices will be followed.

#### **3.6.3 Endovascular Access Procedure**

The type of endovascular procedure and the indication for treatment will be recorded. The procedure will be performed according to the institution's standard practices.

#### **3.6.4 Vital Signs**

Blood pressure, heart rate, respiration, temperature.

#### **3.6.5 CT Scans**

CT scans (with or without contrast) will be optimally (not mandatory) performed prior to the endovascular access procedure to assess for the presence of prior recent bleeding events or vascular complications (i.e. pseudonaeurysm, fistula). Following the procedure, a CT scan (without contrast, unless otherwise indicated) will be performed to confirm or identify any bleeding events. Reference the Imaging Acquisition Protocol in the Study Procedures Manual.

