#### 4.3.3 Post-Endovascular Procedure

After completion of the endovascular procedure the following assessments and procedures will be performed:

- Saranas EBBMS monitoring for up to 8 hours post-procedure
- A non-contrast CT scan (or contrast CT if clinically indicated or preferred) to identify or confirm any bleeds
- CBC, PT, PTT, INR, creatinine and activated clotting time should be collected immediately before removal of the Saranas EBBMS
- Removal of Saranas EBBMS
- Recording of adverse events and/or device complications
- Recording of the number of units of blood transfused
- Prior to discharge, serum CBC, PT, PTT, INR and creatinine
- Subject will be discharged
- Return of device to sponsor for assessment of impedance response.

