## **6.0 STATISTICAL CONSIDERATIONS**

### **6.1 Patient Sample Size Requirements**

This study is intended to describe the accuracy and safety of the Saranas EBBMS. A sample of approximately 100 subjects should provide adequate evaluation of the planned endpoints. If 5%,  $n = 5$ , of subjects experience a bleed as detected by either the Saranas EBBMS or computerized tomography then the Kappa score remains above 0.7 when there are two or fewer discordant pairs. The 95% confidence interval with two discordant pairs and Kappa of 0.74 ranges from 0.39 to 1.0.

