### **6.6.2 Assessment of Endpoints**

#### Primary Endpoint

The primary endpoint is the level of agreement in bleeding detection between the Saranas EBBMS and post-procedural computerized tomography. Each case will be defined dichotomously as bleed or no bleed by both techniques. This analysis will be conducted in the PP population of subjects who has a post-procedure computerized tomography.

Level of agreement will be assessed using Cohen Kappa statistic. A 95% confidence interval will be applied. A good Kappa score is considered to be at 0.6 or greater. for dichotomous endpoints. Each case will be defined as a bleed or no bleeding.

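### The supplied protocol and SAP do not require the post-procedure CT, the sole comparator for the primary kappa, to be read without knowledge of the EBBMS result

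*Combined protocol and SAP*

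**What the plan says.** Section 6.6.2 makes agreement between EBBMS and post-procedure CT the primary endpoint, analysed by Cohen's kappa with a 95% confidence interval in subjects who had the scan. On the classification it says: "Each case will be defined dichotomously as bleed or no bleed by both techniques". On interpretation it says: "A good Kappa score is considered to be at 0.6 or greater". The same CT call is the comparator for the CT-only sensitivity and specificity, and CT severity is one of the variables related to the EBBMS level.

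On the scan itself, section 3.6.5 states: "Following the procedure, a CT scan (without contrast, unless otherwise indicated) will be performed to confirm or identify any bleeding events". Section 4.3.3 lists "A non-contrast CT scan (or contrast CT if clinically indicated or preferred) to identify or confirm any bleeds". Section 3.6.5 then points to an Imaging Acquisition Protocol in the Study Procedures Manual, which is not among the supplied documents.

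On who may know the device result, section 3.5 states: "This is a multi-center, open-label study to evaluate use of the Saranas EBBMS for detection of access site-related internal bleeding events". Section 2.2 describes three alarm levels signalled by LEDs and sound to the attending physician. Section 4.3.3 allows EBBMS monitoring for up to 8 hours after the procedure and does not fix when in that period the CT is taken or read.

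The supplied text does not say who reads the CT, whether the reader may know the EBBMS result, when the read is recorded, or what finding on CT counts as a bleed.

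**The concern.** An agreement study needs two calls made independently. If the person calling the CT knows that the device alarmed, an equivocal finding is more likely to be called a bleed. If the reader knows that the device stayed silent, the same finding is more likely to be dismissed. Either error turns a discordant pair into a concordant one, so kappa rises with no gain in device accuracy. The absence of a stated CT criterion for a bleed leaves the reader more room for this.

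The plan expects few bleeds, so each read carries much weight. No analysis can remove the effect afterwards, because the unmasked call would be the only one on record.

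**Working it through.** **Inputs.** From section 6.1: "A sample of approximately 100 subjects should provide adequate evaluation of the planned endpoints"; and the supposition that 5% (n = 5) "of subjects experience a bleed as detected by either the Saranas EBBMS or computerized tomography then the Kappa score remains above 0.7" provided no more than two pairs are discordant. From section 6.6.2: the 0.6 benchmark. Not in the documents, so assumed: how many pairs would be discordant under a masked read, and how many reads would be moved.

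**Formula.** Let a = positive on both, b = device only, c = CT only, d = negative on both, n = 100. Then p_o = (a + d)/n, p_e = [(a + b)(a + c) + (c + d)(b + d)]/n², and kappa = (p_o − p_e)/(1 − p_e). Tables are written (a, b, c, d).

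**1. The plan's own figure.** Section 6.1 states: "The 95% confidence interval with two discordant pairs and Kappa of 0.74 ranges from 0.39 to 1.0". For (3, 1, 1, 95), p_o = 0.98 and p_e = (4×4 + 96×96)/10,000 = 0.9232, so kappa = 0.0568/0.0768 = 0.740. With the large-sample standard error of 0.177 the 95% interval is 0.39 to 1.09, capped at 1.0. The splits (3, 2, 0, 95) and (3, 0, 2, 95) also give 0.740. The stated figures reproduce.

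**2. One read moved, starting from the plan's two-discordant case (3, 1, 1, 95).**
- The device-only case is re-read as CT-positive, giving (4, 0, 1, 95): p_e = (4×5 + 96×95)/10,000 = 0.9140; kappa = 0.076/0.086 = 0.884.
- The CT-only case is re-read as negative, giving (3, 1, 0, 96): p_e = (4×3 + 96×97)/10,000 = 0.9324; kappa = 0.0576/0.0676 = 0.852.

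**3. One read moved, starting from three discordant pairs (assumed).** With 5 positive by either method, take (2, 2, 1, 95) as the masked result. Then p_o = 0.97 and p_e = (4×3 + 96×97)/10,000 = 0.9324, so kappa = 0.0376/0.0676 = 0.556 (95% interval 0.11 to 1.00).
- One device-only case is re-read as CT-positive, giving (3, 1, 1, 95): kappa 0.740.
- The CT-only case is re-read as negative, giving (2, 2, 0, 96): p_e = (4×2 + 96×98)/10,000 = 0.9416; kappa = 0.0384/0.0584 = 0.658.

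**4. CT-only sensitivity and specificity for the tables in step 3.** The masked values are 2/3 and 95/97 (97.9%). After the first flip they are 3/4 and 95/96 (99.0%). After the second they are 2/2 and 96/98 (98.0%).

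**5. Range over assumed accuracy.** Suppose the device has 80% sensitivity and 95% specificity against a masked CT read. The table shows kappa at the expected cell proportions when a given share of discordant reads follows the device. None of these inputs is in the documents.

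| Bleed prevalence | 0% | 10% | 25% | 50% |
|---|---|---|---|---|
| 5% | 0.55 | 0.61 | 0.68 | 0.80 |
| 20% | 0.75 | 0.77 | 0.81 | 0.88 |

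Kappa rises in each case, and by more when bleeds are rarer.

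**The case against.** Several stronger readings are tempting, and the documents do not support them.

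- *The plan sends alarm patients to CT for confirmation.* A reader might infer this from the word confirm. Sections 3.6.5 and 4.3.3 pair it with identifying bleeds, and the synopsis plans the scan for all subjects if medically possible. Section 5.5.2 also uses the CT as a safety check before release. The scan is not triggered by the alarm.
- *The plan has the CT reader told the device result.* It is silent. Open-label describes the study as a whole, and section 2.2 directs the alarm to the attending physician. No section places the CT reader with that physician.
- *No reading rule exists anywhere.* The Study Procedures Manual could contain one. The item cited from it is, by its title, about acquiring images.
- *Every CT read is exposed.* An alarm after the read cannot affect it. With monitoring of up to 8 hours and no fixed CT time, exposure is partial and unknown.
- *One read could turn failure into success.* The 0.6 value is a descriptive benchmark, with interpretation bands in Table 7, and section 6.1 says that the study is meant to describe accuracy and safety. No decision rule depends on 0.6. The three-discordant starting point is this review's assumption; in the plan's two-discordant example kappa is already above 0.6.
- *All accuracy measures must rise.* From (2, 3, 0, 95), with kappa 0.56, CT sensitivity is 100% before and after a device-only flip. Only kappa (to 0.74) and specificity (95/98 to 95/97) increase.

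These points limit the concern without removing it. A safeguard on which the primary comparator depends should be visible in the protocol and SAP, even if only as a cross-reference.

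**Conclusion.** The concern holds in this form. As written, the plan allows the sole comparator for the primary kappa and for the CT-only sensitivity and specificity to be read with the EBBMS result in view. The bias would favour agreement. The documents show that it is possible, not that it will occur, and they do not allow its size to be estimated.

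The calculation shows how much rests on one read: in the tables worked here, a single flip moves kappa by about 0.10 to 0.18. This rests on the plan's 100 subjects and 5 positives, on two (the plan's) or three (assumed) discordant pairs, and on one read being moved (assumed). The intervals are wide and overlap heavily, so such a shift would be hard to recognise in the results.

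The secondary endpoints that combine clinical assessment with CT raise a separate question, because there the clinical determination of a bleed overrules the CT.

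**What to change.** - **Sections 3.6.5 and 4.3.3.** State that study CT requests use the same wording for every subject and omit EBBMS status. State that the reader the site already uses records and locks the bleed/no-bleed call and the CT severity on the CRF before being given any EBBMS result.
- **Section 6.6.2.** Base the primary kappa and the CT-only endpoints on that locked read.
- **Patient care.** State that a clinical read with full information may proceed at any time and is never delayed by the study read, but does not replace the locked call.
- **CRF.** Record whether the reader knew the EBBMS status. Masking may be imperfect, since actions taken after an alarm, which section 4.3.2 records, can hint at it.
- **If the Study Procedures Manual already contains such rules,** cite them in these sections.

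The cost is protocol wording, a request template and one CRF step. No additional scan and no change in sample size are needed, and the proposal does not call for an independent reader. Because the documents do not name the reader, it is an assumption that the existing one can make the locked call at every site.

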#### **3.6.6 Bleeding, Vascular Complications, and Acute Kidney Injury Assessment**

The VARC-2 definitions will be used for bleeding severity and vascular complications, refer to [Table 4](#) and [Table 5](#). For classification of acute kidney injury refer to the AKIN Classification in [Table 6](#).

**Table 4. VARC-2 Definitions Bleeding Severity**

---

**Life-threatening or disabling bleeding**

- Fatal bleeding OR
- Bleeding in a critical organ, such as intracranial, intraspinal, intraocular, or pericardial necessitating pericardiocentesis, or intramuscular with compartment syndrome OR
- Bleeding causing hypovolemic shock or severe hypotension requiring vasopressors or surgery OR
- Overt source of bleeding with drop in hemoglobin  $>5$  g/dL or whole blood or packed red blood cells (RBCs) transfusion  $>4$  units)\*

**Major bleeding**

- Overt bleeding either associated with a drop in the hemoglobin level of at least 3.0 g/dL or requiring transfusion of two or three units of whole blood/RBC, or causing hospitalization or permanent injury, or requiring surgery AND
- Does not meet criteria of life-threatening or disabling bleeding

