**Minor bleeding**

- Any bleeding worthy of clinical mention (e.g. access site hematoma) that does not qualify as life-threatening, disabling, or major

---

*\*Given that one unit of packed RBC typically will raise the hemoglobin concentration by 1 g/dL, an estimated decrease in hemoglobin will be calculated.*

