### **Table 6. Acute Kidney Injury (AKIN Classification)**

#### **Stage 1**

- Increase in serum creatinine to 150–199% (1.5–1.99 x increase compared with baseline) OR increase of >0.3 mg/dl (>26.4 mmol/l)

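### Table 4 gives no transfusion class to exactly four units, so a four-unit bleed with a small hemoglobin drop can be graded Minor, below a two-unit bleed

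*Combined protocol and SAP*

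**What the plan says.** Section 3.6.6 adopts the VARC-2 bleeding classes set out in Table 4.

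- **Life-threatening or disabling.** One line combines a hemoglobin criterion, "Overt source of bleeding with drop in hemoglobin" of more than 5 g/dL, with a transfusion criterion, "packed red blood cells (RBCs) transfusion $>4$ units". This line carries the table's only asterisk. Fatal bleeding, critical-organ bleeding, and shock or severe hypotension needing vasopressors or surgery also qualify.
- **Major.** The criteria are a "drop in the hemoglobin level of at least 3.0 g/dL", or bleeding "requiring transfusion of two or three units of whole blood/RBC", "or causing hospitalization or permanent injury, or requiring surgery", provided the higher class is not met.
- **Minor.** This is the residual class: any bleed worth clinical mention "that does not qualify as life-threatening, disabling, or major".
- **Footnote.** An estimated hemoglobin decrease is to be calculated, on the basis that one unit of packed cells raises hemoglobin by about 1 g/dL.

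Section 6.6.2 relates EBBMS level to VARC-2 severity and, as a separate endpoint, to the number of transfusions. Tabulations, summary statistics and interclass correlations are planned for both. Section 4.3.3 has the units transfused recorded.

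Table 6 gives the AKIN creatinine thresholds in two units. Stage 1 reads "increase of >0.3 mg/dl (>26.4 mmol/l". Stage 3 pairs 4.0 mg/dl with 354 mmol/l and 0.5 mg/dl with 44 mmol/l.

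**The concern.** The two transfusion rules do not meet. Two or three units is Major and five or more is life-threatening, but no rule names four. Because Minor is defined by exclusion, a four-unit subject who meets nothing else lands there, and the severity scale is no longer ordered by transfusion.

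What is at stake is the coding of one secondary variable. In the analysis by number of transfusions, a four-unit subject ranks above a two-unit subject. In the VARC-2 analysis the same pair can rank the other way round. With few bleeds, one reversed subject could change a tabulation or a correlation. Settling the class only after EBBMS levels are known would also invite a question about how it was chosen.

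**Working it through.** **Table 4.** There is no calculated figure in the plan to reproduce here, so the check applies the printed rules.

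Inputs, all from Table 4: life-threatening if the drop is >5 g/dL or units >4; Major if the drop is ≥3.0 g/dL or units are 2 or 3; otherwise Minor. Let *u* be whole units, *o* the observed drop in g/dL, and *e* = *o* + 1 × *u* the footnote's estimated drop. Assume no other criterion (shock, vasopressors, surgery, hospitalization, permanent injury) is met. There are three readings of the footnote:

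- A: ignored; *o* is used in both classes.
- B: as marked; *e* is used for life-threatening and *o* for Major.
- C: *e* is used in both classes.

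Class by units at *o* = 1.0 g/dL (LT = life-threatening):

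| Units | 0 | 1 | 2 | 3 | 4 | 5 | 6 |
|---|---|---|---|---|---|---|---|
| A | Minor | Minor | Major | Major | **Minor** | LT | LT |
| B | Minor | Minor | Major | Major | **Minor** | LT | LT |
| C | Minor | Minor | Major | Major | Major | LT | LT |

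The four-unit subject as the observed drop varies:

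| *o* (g/dL) | *e* = *o* + 4 | A | B | C |
|---|---|---|---|---|
| -1.5 | 2.5 | Minor | Minor | Minor |
| 0 | 4.0 | Minor | Minor | Major |
| 1.0 | 5.0 | Minor | Minor | Major |
| 1.1 | 5.1 | Minor | LT | LT |
| 3.0 | 7.0 | Major | LT | LT |

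Under B, the reading the asterisk supports, the step from 1.0 to 1.1 g/dL moves the subject two classes. Major cannot be reached through hemoglobin or units: *o* ≥ 3.0 gives *e* ≥ 7.0, which is already above 5. A two-unit subject with *o* = 1.0 has *e* = 3.0 and is Major by unit count.

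The footnote's scope matters away from four units too. One unit with *o* = 2.0 gives *e* = 3.0, which is Minor under B and Major under C.

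**Table 6.** Formula: mmol/l = mg/dl × 10 / molar mass, taking creatinine as 113.12 g/mol (a physical constant that the documents do not give, so an assumption).

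| mg/dl | Calculated mmol/l | Calculated micromol/l | Printed as mmol/l | Printed ÷ calculated mmol/l |
|---|---|---|---|---|
| 0.3 | 0.0265 | 26.5 | 26.4 | 995 |
| 4.0 | 0.354 | 354 | 354 | 1,001 |
| 0.5 | 0.0442 | 44.2 | 44 | 995 |

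The printed numbers are reproduced, to rounding, only in micromol/l. Read literally, 354 mmol/l would be 354 × 113.12 / 10 = about 4,004 mg/dl.

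**The case against.** Four points can be made on the other side.

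1. *A sign may have been lost.* The Table 4 gap turns on one character, an at-least sign that could have become a greater-than sign in conversion from PDF. The Table 6 error likewise turns on a micro sign that could have become an m. At-least signs do survive in the eligibility criteria, and a micro sign survives in the Instructions for Use, so the printed text is the better reading. Those places are not these tables, however. Table 6 also has a similar boundary gap: Stage 2 ends at 299% and Stage 3 starts above 300%. The doubt stands, and only the source PDF can settle it.

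2. *The footnote may be meant for the whole table.* It is worded without restriction and printed beneath all three classes. Read that way (C), four units is Minor only if hemoglobin rose by more than 1 g/dL, so the gap nearly closes. The asterisk's placement points the other way, and nothing in the text extends the footnote to the Major line.

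3. *Class does not rest on transfusion alone.* This is correct and limits the point. A reader might infer that every four-unit subject is unclassified or Minor. The table does not support that: an observed drop above 1 g/dL makes the subject life-threatening under B, and shock, vasopressors, surgery, hospitalization or permanent injury each lead to a higher class.

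4. *The units are not lost.* They are recorded and analysed as a separate endpoint. That is true, but it leaves the VARC-2 variable misordered.

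**Conclusion.** The defect is real but narrow. As printed, with the footnote applied where it is marked, a subject with exactly four units, an observed drop of 1 g/dL or less and no other criterion is Minor, below a two-unit subject. Just above 1 g/dL the same subject is life-threatening. This rests on the printed sign being the intended one.

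The only endpoint in section 6.6.2 that uses the class is the descriptive analysis of EBBMS level against VARC-2 severity. The primary kappa compares bleed or no bleed by EBBMS and CT, and does not use Table 4.

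A reader might take the five bleeds in section 6.1 and conclude that one such subject distorts one of five severity values. That is not supported. The five are an assumed count of bleeds seen by EBBMS or CT, not of transfused or VARC-2-graded subjects, and the documents give no frequency for four-unit transfusions.

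The Table 6 error, a factor of about 1,000, is clerical. The mg/dl value stands beside each figure, all sites are in the US, and the endpoint is the occurrence of kidney injury. No effect on results is expected.

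**What to change.** - Check the life-threatening transfusion line of Table 4 against the source PDF and the cited VARC-2 definition. If a sign was lost, the transfusion part of this point falls away; the footnote question remains.
- Otherwise, reconcile the three classes so that every transfusion count falls in exactly one of them and severity never decreases as units rise. Placing four units explicitly in either the Major or the life-threatening class would do this. Which one applies is for the sponsor to settle from the cited definition.
- State whether the estimated-hemoglobin footnote also applies to the Major criterion of 3.0 g/dL.
- In Table 6, change mmol/l to micromol/l in Stages 1 and 3.

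The cost is edits to two tables, best made before any subject is graded. No new data are needed, since units and hemoglobin are already collected, and nothing changes at the sites.

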**Minor bleeding**

- Any bleeding worthy of clinical mention (e.g. access site hematoma) that does not qualify as life-threatening, disabling, or major

---

*\*Given that one unit of packed RBC typically will raise the hemoglobin concentration by 1 g/dL, an estimated decrease in hemoglobin will be calculated.*

**Table 5. VARC-2 Definitions Vascular Complications**

---

**Major Vascular Complications**

1. Any aortic dissection, rupture, left ventricular perforation, or new apical aneurysm/pseudoaneurysm
2. Access site or access-site related vascular injury (dissection, perforation, stenosis, hematoma, etc.) leading to death, life-threatening or major bleeding, visceral ischemia, or neurological impairment
3. Distal embolization requiring vascular surgery, amputation, or irreversible end organ damage
4. Unplanned endovascular or surgical intervention associated with death, major bleeding, visceral ischemia, or neurological impairment
5. Any new ipsilateral lower extremity ischemia
6. Surgery for access site-related nerve injury
7. Permanent access site-related nerve injury

